### **5.2 Randomization**

Consenting subjects will be randomized up to 7 days after baseline visit. Treatment allocation is determined by central web-randomization. A randomization list has been generated by the trial statistician prior to embarking on the trial. Randomization is in permuted blocks of 10, prepared using random number tables, and is stratified according to laboratory criteria ('High-risk' versus 'Non-high risk' laboratory groups, defined below) and the timing of pregnancy loss (late loss versus no late loss) Any past history of loss  $\geq$  10 weeks gestation will be included in the late loss group.

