**5.3 Web Base Randomization**

The randomization process is started by the local study personnel (investigator or study coordinator) who initiates a randomization request by accessing the APPLE webpage and randomization request form. This portion of the webpage requires authorised users to enter a username and password. To randomize a subject the following information is required: category of 'high' versus 'non-high' risk laboratory criteria, and category of early versus late pregnancy loss. The program will request that the information entered be verified for accuracy and will prompt any errors or missing fields to be completed. When the information is accepted, the program will provide the delegated study coordinators, Qualified Investigator, and pharmacy team the treatment allocation by using the next allocation from that block.

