#### **8.1.4. Full Trial Analyses**

Several secondary outcomes will be collected in the pilot trial, which will be included in the analysis of the full trial if there are no significant changes to the trial design.

**Primary analysis:** Analysis will be performed by intention to treat. Intention to treat analysis will be supplemented by a sensitivity analysis that excludes subjects who did not complete the allocated treatment plan. The live birth rate will be compared in the experimental and standard of care arm by an unadjusted Fisher's test of proportions, with 95% confidence intervals provided.

**Secondary analysis:** Analysis will be performed by intention to treat. Intention to treat analysis will be supplemented by a sensitivity analysis that excludes subjects who did not complete the allocated treatment plan. Proportions will be compared between study arms by an unadjusted Fisher's test, with 95% confidence intervals reported. The following outcomes will be analyzed: Pregnancy loss by central laboratory testing, pregnancy loss by gestational age (<10 weeks, 10-19 weeks,  $\geq$ 20 weeks gestation), pre-eclampsia, early onset pre-eclampsia, severe pre-eclampsia, SGA <10th percentile, SGA <5th percentile, SGA <3rd percentile, placental abruption requiring delivery, pre-term delivery <37 weeks gestation, symptomatic VTE, symptomatic ATE, major bleeding, clinically relevant non-major bleeding, non-major non-CRNMB, major peripartum bleeding, minor peripartum bleeding, HIT, symptomatic fracture, allergic reaction, and all-cause mortality.

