### **8.2 Determination of Sample Size**

The sample size of the pilot trial is 24 participants, based on a recruitment rate of 1 participant per 2 months per site. This sample size was derived based on the full trial sample size, which factored in that these 2 sites are highly motivated and will have higher recruitment rates compared to other potential sites.

The full trial sample size is 828 participants, which is based on a 60% absolute event rate in the ASA arm, minimal clinically important difference (MCID) of 10%, 80% power at alpha 0.05, and a drop-out rate of 10%. The MCID was determined based on a survey of 22 physicians (20% response rate) among CanVECTOR Network and Thrombosis Canada members.

With involvement from 40 centers over 5 years, this sample size calculation of 828 equates to 4 participants per year per center, however, we acknowledge that the 2

pilot sites are highly motivated and will have higher recruitment rates on average, therefore we have set a minimum recruitment rate of 1 patient per 2 months per site.

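### Randomisation is stratified on two factors, but full-trial live birth is tested by an unadjusted Fisher's test: valid and powered as planned, yet less efficient than a stratified test at the same N

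*Combined protocol and SAP*

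**What the plan says.** Section 5.2 says that randomisation "is stratified according to laboratory criteria ('High-risk' versus 'Non-high risk' laboratory groups, defined below) and the timing of pregnancy loss". Crossing the two factors gives Groups A to D, in permuted blocks of 10. Section 5.3 makes both factors compulsory entries before an allocation is released: "category of 'high' versus 'non-high' risk laboratory criteria, and category of early versus late pregnancy loss".

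For the full trial, section 8.1.4 says: "The live birth rate will be compared in the experimental and standard of care arm by an unadjusted Fisher's test of proportions". For the secondary outcomes: "Proportions will be compared between study arms by an unadjusted Fisher's test, with 95% confidence intervals reported". Both are by intention to treat, with a sensitivity analysis that drops women who did not complete the allocated plan. No analysis adjusted for, or stratified by, the randomisation factors appears anywhere. The outcome broken down by central laboratory results (sections 2.5 and 8.1.4) is not an adjustment. It uses central results rather than the category entered at randomisation, and it leaves out late loss.

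Section 8.2 gives the size: "The full trial sample size is 828 participants, which is based on a 60% absolute event rate in the ASA arm", with a minimal important difference of 10%, 80% power, alpha 0.05 and 10% drop-out.

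**The concern.** The sponsor thought laboratory risk and late loss important enough to balance by design, but the analysis then discards them. Stratified allocation removes chance imbalance between arms on these factors. An unstratified test still computes its variance as if that imbalance could occur. If the factors predict live birth, the test becomes conservative and some power is given up. Fisher's exact test adds conservatism of its own.

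Two outcomes would have been serious: a type I error above 5%, or a full trial short of its planned power. The check below looks for both, and then at how much a stratified test would gain. The full trial is planned for 40 centres over 5 years and recruitment is the acknowledged difficulty, so power that costs no participants is worth having.

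**Working it through.** **Inputs.** From section 8.2: 60% live birth on ASA, 10-point difference, 80% power, alpha 0.05, 10% drop-out, N = 828. Taken as 60% v 70%, two-sided and 1:1, none of which is stated outright. The alternatives do not give 828: with continuity correction and drop-out added as × 1.10, 60% v 50% gives 898 and a one-sided test gives 660. One-to-one allocation fits the interim look at 16 women with 8 per arm (sections 11.1 and 11.2). Stratum sizes and live birth rates are not in the documents and are assumed over a range.

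**1. Reproduce 828.** With mean rate 0.65:

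- Uncorrected: n = [1.960 × √(2 × 0.65 × 0.35) + 0.842 × √(0.60 × 0.40 + 0.70 × 0.30)]² / 0.10² = 355.9, so 356 per arm.
- Continuity-corrected: n′ = (355.9 / 4) × [1 + √(1 + 4 / (355.9 × 0.10))]² = 375.7, so 376 per arm.
- 2 × 376 = 752, and 752 × 1.10 = 827.2, rounded up to 828.

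The continuity-corrected formula approximates Fisher's exact test, so the size matches the planned test.

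**2. Fisher's power and size, by exact enumeration.** At 376 per arm, power is 80.3%. After 10% drop-out, 828 × 0.90 / 2 = 372.6, taken as 372 per arm, where Fisher has 79.7% power and the uncorrected chi-square 81.8%. Fisher's type I error at 372 per arm is 4.10%, 4.19% and 4.15% at common rates of 60%, 65% and 70%. The small dip below 80% arises because drop-out was added as × 1.10 rather than ÷ 0.90.

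**3. Why stratified allocation makes the unadjusted test more conservative.** The test uses variance p(1 − p) = 0.60 × 0.40 = 0.240. With strata balanced, the relevant variance is 0.240 less the between-stratum variance of the rates. For rates of 75/65/55/45% that variance is (0.0225 + 0.0025 + 0.0025 + 0.0225) / 4 = 0.0125, leaving 0.2275. For 80/70/50/40% it is 0.025, leaving 0.215. For 66/62/58/54% it is only 0.002, leaving 0.238.

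**4. Power with strata.** 372 per arm, +10 points in every stratum, 200,000 simulated trials per row, exact two-sided Fisher on each trial, chi-square and CMH without continuity correction. Simulation error in power is about √(0.8 × 0.2 / 200,000) = 0.1 point. Type I error is simulated with both arms at the ASA-arm rates.

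| ASA-arm rates, four equal strata | Fisher power | Chi-square power | CMH power | Fisher type I error |
|---|---|---|---|---|
| all 60% | 79.7% | 81.8% | 81.9% | 4.1% |
| 66/62/58/54% | 79.9% | 81.9% | 82.1% | 4.0% |
| 75/65/55/45% | 80.4% | 82.5% | 84.0% | 3.5% |
| 80/70/50/40% | 81.0% | 83.1% | 85.9% | 3.0% |

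CMH holds its type I error at 4.9 to 5.0% throughout. Repeat runs agree closely; the largest difference is 3.2% instead of 3.0% for Fisher's error in the last row.

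**5. Split the gain.** Chi-square minus Fisher is about 2 points in every row. CMH minus chi-square, the part due to the strata, is about 0, 0.1 to 0.2, 1.5 and 2.8 points. With unequal strata (10/10/40/40% of women, ASA-arm rates 81/71/61/51%) the powers are 80.3, 82.4 and 83.3%, so even a 30-point spread adds only about 1 point.

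**6. The continuity correction in participants.** Without it, 2 × 356 = 712 and 712 × 1.10 = 783.2, rounded up to 784: 44 fewer than 828. This is the price of sizing for a Fisher-type test, not the effect of stratifying.

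**The case against.** The strongest reply is that nothing is broken. The sponsor chose an unadjusted test, sized the trial for it, and the two agree. Much of the gain is also not due to stratification: about 2 points would come from an unstratified chi-square. Against a CMH test with continuity correction, power is 79.6, 80.0, 81.8 and 84.1% in the four equal-strata scenarios, so with weak strata the advantage over Fisher disappears. The larger gains need 30- to 40-point spreads in live birth across strata, which the documents do not support with data, and equal strata are doubtful given the narrow definition of the non-high-risk laboratory group. If outcomes prove nearly complete, Fisher has up to 84.0% power at 414 per arm. Finally, this is a 24-participant feasibility pilot, and the full trial is conditional on its success.

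All of this stands as a limit on size and importance. It does not remove the point. Even the continuity-corrected CMH test is essentially no worse than Fisher in any scenario, the uncorrected version keeps its error at about 5%, and the stratum data are already collected. The plan gives no reason for leaving the factors out.

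**Conclusion.** The point holds as a modest matter of efficiency, not as an error of validity or sample size. Type I error stays below 5%, and the planned 80% power is met to rounding (79.7% at 372 per arm, 80.3% at 376). At the same N, an uncorrected CMH test over the randomisation strata would give about 82 to 86% power. About 2 points of the gain come from replacing Fisher's test, and 0 to about 3 from the strata.

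The first part depends on using CMH without continuity correction. The second depends on assumed stratum rates and sizes and could be zero. The calculation also assumes 60% v 70%, a two-sided test, 1:1 allocation and the same 10-point difference in every stratum. Nothing changes for the pilot's primary analysis of recruitment (section 8.1.2).

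**What to change.** Reword section 8.1.4 before pilot outcomes are carried into the full trial, so that the choice cannot be seen as driven by the data:

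- **Primary analysis:** a CMH test of live birth over the four strata as entered at randomisation, stated to be without continuity correction, with the Mantel-Haenszel common risk difference and its 95% confidence interval. This also settles the interval method, which the plan leaves unnamed.
- **Common secondary outcomes:** the same method.
- **Fisher's test:** keep it as a supportive analysis of live birth, and as the test for rare outcomes such as HIT, fracture and death.

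The cost is wording in 8.1.4. Both factors are already required by the randomisation form in section 5.3, and N can stay at 828.

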### **8.2 Determination of Sample Size**

The sample size of the pilot trial is 24 participants, based on a recruitment rate of 1 participant per 2 months per site. This sample size was derived based on the full trial sample size, which factored in that these 2 sites are highly motivated and will have higher recruitment rates compared to other potential sites.

The full trial sample size is 828 participants, which is based on a 60% absolute event rate in the ASA arm, minimal clinically important difference (MCID) of 10%, 80% power at alpha 0.05, and a drop-out rate of 10%. The MCID was determined based on a survey of 22 physicians (20% response rate) among CanVECTOR Network and Thrombosis Canada members.

With involvement from 40 centers over 5 years, this sample size calculation of 828 equates to 4 participants per year per center, however, we acknowledge that the 2

pilot sites are highly motivated and will have higher recruitment rates on average, therefore we have set a minimum recruitment rate of 1 patient per 2 months per site.

## **9. QUALITY ASSURANCE (QA)**

### **9.1. Quality Assurance**

Quality assurance at trial sites will be supported through training and monitoring. At each site this will consist of an initiation visit or teleconference, ongoing training (as needed), central and on-site monitoring, and a close-out visit or teleconference. Details about the process and content of the initiation and close-out visits are included in the Resource Manual.

### **9.2 Monitoring**

Study monitoring is a sponsor responsibility that ensures that the rights and well-being of human subjects are protected, the reported trial data are accurate, complete, and verifiable from source documents, and that the conduct of the trial complies with the protocol, GCP, and regulatory requirements.

Monitoring for the trial will be performed by the sponsor, according to the detailed monitoring plan for the trial.

## **10. ETHICS**

### **10.1 Ethical Conduct of the Trial**

The trial will be performed in accordance with the recommendations guiding physicians in biomedical research involving human subjects adopted by the 18th World Medical Assembly (Helsinki, Finland, 1964 and later revisions), the Tri-Council Policy Statement and the ICH GCP Guidelines.

### **10.2 Research Ethics Board (REB)**

REB approval will be obtained and maintained annually with OHSN-REB, the REB board of record, through CTO.

### **10.3 Subject Information and Consent**

The investigator, or his designee, will inform each subject (or the subject's acceptable representative) prior to inclusion in the trial, full and adequate verbal and written information regarding the objective and procedures of the trial and the possible risks involved. The subjects must be informed about their right to withdraw from the trial at any time. Written subject information will be given to each subject before enrolment. Furthermore, it is the responsibility of the investigator or his designee to obtain signed informed consent from all subjects prior to inclusion in the trial.

## **11. DATA SAFETY MONITORING BOARD**

### **11.1 Data Safety Monitoring Board (DSMB)**

A DSMB will complete a safety analysis after 16 patients are recruited with a pre-defined stopping rule. The DSMB Terms of Reference outline the DSMB operating procedures.

## **11.2. Interim Stopping Rule**

The pilot study will be halted early if 0 out of 8 subjects in either arm have a live birth. The upper bound of the confidence interval is 32.4%, which would be lower than expected. If only 1/8 patients had a live birth, while the point estimate is 12.5%, the upper bound of the 95th confidence interval is 47.1%, which is still in the realm of expected results.

# **12. DATA HANDLING AND RECORD KEEPING**

## **12.1 Personal Health Information**

Medical records will be reviewed in compliance with applicable provincial privacy laws as well as local hospital privacy policies. All personal health information will be treated in a confidential manner with respect to its collection, use, and disclosure. Participant names or potentially identifying personal health information will not leave the institution. Any source documents provided to the sponsor for monitoring purposes must first be de-identified. The consent form will describe to the participant who will have access to their information and for what purposes (e.g., Health Canada, Research Ethics Board (REB), research sponsors and personnel monitoring/auditing the research on their behalf). A master list that links participant identities to their unique participant numbers will be maintained at all study sites and stored separately from all other study records.

## **12.2 Case Report Forms**

A Case Report Form (CRF) is required and will be completed for each randomized subject. The completed original CRFs are the sole property of The Ottawa Hospital and are not to be made available in any form to third parties, except for authorized representatives of appropriate Regulatory Authorities.

## **12.3 Record Retention**

To enable evaluations and/or audits, the investigator will keep records according to section 8.0 in ICH/GCP, including the identity of all participating subjects (sufficient information to link records, e.g., CRFs and hospital records), all original signed Informed Consent Forms and source documents, copies of all CRFs and detailed records of drug disposition. To comply with Canadian regulations, the records are to be retained for 25 years.

